7.2.5.4.1 Survival Follow-up

Once a subject experiences confirmed disease progression or starts a new anti-cancer therapy, the subject moves into the survival follow-up phase and should be followed every 12 weeks to assess for survival status until death, withdrawal of consent, or the end of the study, whichever occurs first.

7.3 Assessing and Recording Adverse Events

An adverse event is defined as any untoward medical occurrence in a patient or clinical investigation subject administered a pharmaceutical product and which does not necessarily have to have a causal relationship with this treatment. An adverse event can therefore be any unfavorable and unintended sign (including an abnormal laboratory finding, for example), symptom, or disease temporally associated with the use of a medicinal product or protocol-specified procedure, whether or not considered related to the medicinal product or protocol-specified procedure. Any worsening (i.e., any clinically significant adverse change in frequency and/or intensity) of a preexisting condition that is temporally associated with the use of the study intervention, is also an adverse event.

Changes resulting from normal growth and development that do not vary significantly in frequency or severity from expected levels are not to be considered adverse events. Examples of this may include, but are not limited to, teething, typical crying in infants and children and onset of menses or menopause occurring at a physiologically appropriate time.

Progression of the cancer under study is not considered an adverse event.

All adverse events that occur after the consent form is signed but before treatment allocation/randomization must be reported by the investigator if they cause the subject to be excluded from the trial, or are the result of a protocol-specified intervention, including but not limited to washout or discontinuation of usual therapy, diet, placebo treatment or a procedure.

From the time of treatment allocation through 30 days following cessation of treatment, all adverse events must be reported by the investigator. Such events will be recorded at each examination on the Adverse Event case report forms/worksheets.

7.3.1 Definition of an Overdose for this Protocol and Reporting of Overdose to the Sponsor and to Merck

For purposes of this trial, an overdose of pembrolizumab will be defined as any dose of 1,000 mg or greater (≥ 5 times the indicated dose). No specific information is available on the treatment of overdose of pembrolizumab. In the event of overdose, the subject should be observed closely for signs of toxicity. Appropriate supportive treatment should be provided if clinically indicated.

If an adverse event(s) is associated with (“results from”) the overdose of a study intervention, the adverse event(s) is reported as a serious adverse event, even if no other seriousness criteria are met.

If a dose of study intervention meeting the protocol definition of overdose is taken without any associated clinical symptoms or abnormal laboratory results, the overdose is reported as a non-serious Event of Clinical Interest (ECI), using the terminology “accidental or intentional overdose without adverse effect.”

All reports of overdose with and without an adverse event must be reported within 24 hours to the Sponsor and within 2 working days hours to Merck Global Safety. (Attn: Worldwide Product Safety; [contact])

7.3.2 Reporting of Pregnancy and Lactation to the Sponsor and to Merck

Although pregnancy and lactation are not considered adverse events, it is the responsibility of investigators or their designees to report any pregnancy or lactation in a subject (spontaneously reported to them) that occurs during the trial.

Pregnancies and lactations that occur after the consent form is signed but before treatment allocation/randomization must be reported by the investigator if they cause the subject to be excluded from the trial, or are the result of a protocol-specified intervention, including but not limited to washout or discontinuation of usual therapy, diet, placebo treatment or a procedure.

Pregnancies and lactations that occur from the time of treatment allocation/randomization through 120 days following cessation of Sponsor’s product, or 30 days following cessation of treatment if the subject initiates new anticancer therapy, whichever is earlier, must be reported by the investigator. All reported pregnancies must be followed to the completion/termination of the pregnancy. Pregnancy outcomes of spontaneous abortion, missed abortion, benign hydatidiform mole, blighted ovum, fetal death, intrauterine death, miscarriage and stillbirth must be reported as serious events (Important Medical Events). If the pregnancy continues to term, the outcome (health of infant) must also be reported.

Such events must be reported within 24 hours to the Sponsor and within 2 working days to Merck Global Safety (Attn: Worldwide Product Safety; [contact]).

7.3.3 Immediate Reporting of Adverse Events to the Sponsor and to Merck

7.3.3.1 Serious Adverse Events

A serious adverse event is any adverse event occurring at any dose or during any use of pembrolizumab that:

- Results in death;
- Is life threatening;
- Results in persistent or significant disability/incapacity;
- Results in or prolongs an existing inpatient hospitalization;
- Is a congenital anomaly/birth defect;

- Is another important medical event

Note: In addition to the above criteria, adverse events meeting either of the below criteria, although not serious per ICH definition, are reportable to Merck in the same timeframe as SAEs to meet certain local requirements. Therefore, these events are considered serious by Merck for collection purposes.

- Is a new cancer (that is not a condition of the study);
- Is associated with an overdose.

For the time period beginning when the consent form is signed until treatment allocation/randomization, any serious adverse event, or follow up to a serious adverse event, including death due to any cause other than progression of the cancer under study that occurs to any subject must be reported within 24 hours to the Sponsor and within 2 working days to Merck Global Safety if it causes the subject to be excluded from the trial, or is the result of a protocol-specified intervention, including but not limited to washout or discontinuation of usual therapy, diet, placebo treatment, or a procedure.

For the time period beginning at treatment allocation/randomization through 30 days following cessation of treatment, whichever is earlier, any serious adverse event, or follow up to a serious adverse event, including death due to any cause other than progression of the cancer under study, whether or not related to the study intervention, must be reported within 24 hours to the Sponsor and within 2 working days to Merck Global Safety.

Additionally, any serious adverse event, considered by an investigator who is a qualified physician to be related to study intervention that is brought to the attention of the investigator at any time following consent through the end of the specified safety follow-up period specified in the paragraph above, or at any time outside of the time period specified in the previous paragraph also must be reported immediately to the Sponsor and to Merck Global Safety.

All subjects with serious adverse events must be followed up for outcome.

SAE reports and any other relevant safety information are to be forwarded to the Merck Global Safety [contact].

7.3.3.2 Events of Clinical Interest

Selected non-serious and serious adverse events are also known as Events of Clinical Interest (ECI) and must be reported within 24 hours to the Sponsor and within 2 working days to Merck Global Safety. (Attn: Worldwide Product Safety; [contact]).

For the time period beginning when the consent form is signed until treatment allocation/randomization, any ECI, or follow up to an ECI, that occurs to any subject must be reported within 24 hours to the Sponsor and within 2 working days to Merck Global Safety if it causes the subject to be excluded from the trial, or is the result of a protocol-specified intervention, including but not limited to washout or discontinuation of usual therapy, diet, placebo treatment or a procedure.

For the time period beginning at treatment allocation/randomization through 90 days following cessation of treatment, or 30 days following cessation of treatment if the subject initiates new anticancer therapy, whichever is earlier, any ECI, or follow up to an ECI, whether or not related to study intervention, must be reported within 24 hours to the Sponsor and within 24 hours to Merck Global Safety.

Events of clinical interest for this trial include:

1. An overdose of study intervention, as defined in Section 7.3.1 - Definition of an Overdose for this Protocol and Reporting of Overdose to the Sponsor, that is not associated with clinical symptoms or abnormal laboratory results.
2. An elevated AST or ALT lab value that is greater than or equal to 3X the upper limit of normal and an elevated total bilirubin lab value that is greater than or equal to 2X the upper limit of normal and, at the same time, an alkaline phosphatase lab value that is less than 2X the upper limit of normal, as determined by way of protocol-specified laboratory testing or unscheduled laboratory testing.*

*Note: These criteria are based upon available regulatory guidance documents. The purpose of the criteria is to specify a threshold of abnormal hepatic tests that may require an additional evaluation for an underlying etiology.

7.3.3.3 Protocol-Specific Exceptions to Serious Adverse Event Reporting

Efficacy endpoints as outlined in this section will not be reported to Merck, unless there is evidence suggesting a causal relationship between the drug and the event. Any such event will be submitted to the Sponsor within 24 hours and to Merck Global Safety within 2 working days either by electronic or paper media.

Specifically, the suspected/actual events covered in this exception include any event that is disease progression of the cancer under study.

The Sponsor will monitor unblinded aggregated efficacy endpoint events and safety data to ensure the safety of the subjects in the trial. Any suspected endpoint which upon review is not progression of the cancer under study will be forwarded to Merck Global Safety as a SAE within 2 working days of determination that the event is not progression of the cancer under study

Hospitalization related to convenience (e.g., transportation issues, etc.) will not be considered a SAE.

7.3.4 Evaluating Adverse Events

An investigator who is a qualified physician will evaluate all adverse events according to the NCI Common Terminology for Adverse Events (CTCAE), version 4.0. Any adverse event which changes CTCAE grade over the course of a given episode will have each change of grade recorded on the adverse event case report forms/worksheets.

All adverse events regardless of CTCAE grade must also be evaluated for seriousness.

7.3.5 Sponsor Responsibility for Reporting Adverse Events

All Adverse Events will be reported to regulatory authorities, IRB/IECs and investigators in accordance with all applicable global laws and regulations.

7.3.5.1 Safety Reporting Requirements for IND Exempt Studies

For Investigator Sponsored IND Exempt Studies there are some reporting requirements for the FDA in accordance with the guidance set forth in 21 CFR 314.80.

7.3.5.2 Reporting to the IRB

Both serious and non-serious adverse events will be reported in accordance with UCD IRB Administration and UCD Comprehensive Cancer Center's Office of Clinical Research (OCR) policies. The UC Davis IRB can be reached at [contact].

Participating site(s) will report adverse events per institution's IRB guidelines.

8.0 CORRELATIVE SCIENCE (Translational Research)

8.1 Rationale

One of the major shortcomings of immunotherapy trials has been the lack of in-depth correlative studies to help identify the mechanism of action and resistance, identify biomarkers of response, and provide a foundation for further improving these approaches. To address this, we plan to perform in depth immunological analysis of mandatory serial patient blood and tumor samples. Tumor biopsies will be obtained pre-treatment and during the final intralesional needle placement for IL-2 delivery. Blood samples will be obtained pre-treatment, after the final dose on intralesional IL-2 and at the first response assessment time point at 6 weeks. We will evaluate immunologic changes systemically and in the tumor microenvironment within patient's pre to post therapy and across the cohort of patients to identify predictive biomarkers and elucidate the mechanistic immunologic effects of therapy and therapy resistance. We will examine putative biomarkers of response to checkpoint immunotherapy such as PD-L1 expression, mutational load, and TILs.

8.1.1 Translational Research Hypothesis

These studies will also evaluate our two mechanistic hypotheses: 1) We hypothesize that the triple combination of radiotherapy + intralesional IL-2 + pembrolizumab will convert patients with primary or secondary resistance to PD-1/PD-L1 blockade into responders by inducing an anti-tumor immune response and overcoming the lack of a pre-existent anti-tumor immune response (e.g., due to a poorly immunogenic tumor or T-cell exclusion from the tumor). 2) We hypothesize that the existence of other dominant modes of immune suppression will limit response to therapy. We will examine hypothesis 1 by evaluating TILs, T cell activation, TCR diversity, and cytokines/chemokines including CCL4. We will examine hypothesis 2 by evaluating immunosuppressive cell subsets, immunosuppressive molecules, and enzymes. Correlative studies will include (in order of priority):

8.1.2 Translational Research Objectives

Blood

- FACS for quantification, immunophenotyping, and functional assessment of PBMCs and immunosuppressive cell subsets
- qPCR (quantitative polymerase chain reaction) evaluation of immune gene signatures including: cytokines, T-cell activation markers, immunosuppressive enzymes and molecules (IDO [indoleamine-pyrrole 2,3-dioxygenase], arginase, CTLA-4, PD-1/PD-L1, Tim-3, LAG3), macrophage polarization, etc.
- Luminex evaluation of plasma for systemic cytokine / chemokine signatures
- T-cell receptor (TCR) deep sequencing to determine clonal expansion of T-cells in the systemic circulation

- Whole exome sequencing of baseline PBMCs as a normal tissue control for tumor whole exome sequencing
- Other studies as deemed feasible and informative by the principal investigators

Tissue

- Multi-plexed IHC / IF to determine the expression of PD-1, PD-L1, CD8, CD4, CD3, IDO, FOXP3, CD68 and others. Automated interaction analysis to determine expression patterns and cell-cell interactions in the TME.
- qPCR evaluation of the tumor microenvironment gene signatures including: cytokines, T-cell activation markers, immunosuppressive enzymes and molecules (IDO, arginase, CTLA4, PD-1/PD-L1), macrophage polarization, etc. qPCR may also be used in a directed manner to confirm results of RNAseq.
- T-cell receptor (TCR) deep sequencing to determine clonal expansion of T-cells in the TME.
- Whole exome sequencing of baseline tumor samples to determine mutational load.
- RNAseq to examine changes in gene expression profiles pre- and post-treatment. RNAseq will also be used to confirm expression of putative tumor mutations identified by whole exome sequencing.
- Other studies as deemed feasible and informative by the principal investigators

8.2 Study Design and Methodology

Details of correlative study sample collection, preparation, and storage are outlined in

Appendix 3. For translational studies tumor tissue will be obtained pre- and post- treatment and peripheral blood will be obtained pre-treatment and at two time points post-treatment from each patient. Thus, a total maximum of 92 fresh tumor biopsies and 138 blood samples will be obtained for this study. We have extensive expertise in all of the techniques described at the UC Davis Laboratory of Tumor Immunology and immune monitoring core.

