2.0 TRIAL DESIGN

Patients with advanced solid malignancies or lymphoma with progression on prior PD-1/L1 blockade will be enrolled. A total maximum of 25 patients will be enrolled.

Primary Objective: Abscopal response rate, ORR, DCR, PFS
Secondary Objective: Maximum tolerated dose (MTD), safety, and toxicity
Collateral Objectives: Immunophenotype serial tumor biopsies and blood samples

Phase I: IL-2 Dose Findin: 3+3 Design: (3-6 patient dose level, 6-18 patients total)				
	Treatment 1 dose	Treatment 2 dose	Treatment 3 dose	Treatment4 dose
Dose Level -1	1 x 10 ⁶ IU	1 x 10 ⁶ IU	1 x 10 ⁶ IU	1 x 10 ⁶ IU
Dose Level 1	3 x 10 ⁶ IU	3 x 10 ⁶ IU	3 x 10 ⁶ IU	3 x 10 ⁶ IU
Dose Level 2	3 x 10 ⁶ IU	7 x 10 ⁶ IU	7 x 10 ⁶ IU	7 x 10 ⁶ IU
Dose Level 3	3 x 10 ⁶ IU	7 x 10 ⁶ IU	15 x 10 ⁶ IU	15 x 10 ⁶ IU

Phase II: IL-2 Dose Expansion Binomial one-Stage Design (18 additional patients; analyzed with patients from MID)	

 P= 0.05, p1= 0.20, r1= 0, n1= 10, rTot=3, nTot=21, a= 0.1, power=0.8 Response will be assessed according to irRECIST and will be evaluated at the non-treatment lesions (abscopal response) 	

CT= computed tomography, DCR=disease control rate, MTD=maximum tolerated dose, ORR=objective response rate, PFS=progression free survival, RT=radiotherapy, P=pembrolizumab,

- a. Patients will be clinically evaluated prior to each cycle of pembrolizumab for the first 3 cycles and weekly during intralesional IL-2 injections, and thereafter every 3 cycles until off treatment.
- b. Laboratory evaluation will occur pre-treatment at every cycle.
- c. For response assessment, patient will have CT imaging pre-treatment and after every three cycles of pembrolizumab.

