At dose escalation levels 2 and 3 and in the phase II portion each patient will receive a test dose of 3×10^6 IU for their first injection prior to escalation to higher doses according to our published guidelines. For example, at dose level 3 each patient will receive an initial test dose of 3×10^6 IU of IL-2, which will be escalated to 7×10^6 for the second treatment and then 15×10^6 IU for the final two treatments as tolerated. If a dose level is not tolerated the treatment will be de-escalated to previous dose levels for subsequent treatments. If 3 million IU IL-2 is not tolerated the dose can be de-escalated to 1 million IU IL-2. If 1 million IU IL-2 is not tolerated the treatment will be deemed intolerable and patient removed from study (see Figure 6).

Patients will be assessed by a physician once during the first week of radiotherapy, weekly during intralesional IL-2 injections, and with every cycle of pembrolizumab. Routine laboratory evaluation will occur pre-treatment. For response assessment patient will have imaging pre-treatment and after every three cycles of Pembrolizumab. For collateral studies patients will undergo mandatory treatment lesion biopsies and blood draws pre-treatment and during the needle placement for the final IL-2 treatment.

Preliminary efficacy as determined by abscopal response rate, ORR, DCR and PFS will be assessed every 3 cycles. Patients on active treatment at 12 months may continue to receive pembrolizumab but will revert to standard of care (SOC) management and be labeled in “follow up”. At this time only PFS and long-term toxicity data will be collected every 3 months.

The primary endpoint is to determine if this regimen converts patients with resistance to PD-1/PD-L1 checkpoint blockade into responders as determined by abscopal response rate (defined as response rate at lesions not treated with RT + IL-2) using irRECIST as well as ORR, DCR, and PFS using RECIST 1.1. The secondary endpoint is tolerability, safety, and toxicity using CTCAE v4.03. Correlative studies include immunophenotyping serial tumor biopsies and blood samples.

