Appendix 3: Molecular Correlative Sample Handling

Specimen Submission for Correlative Studies:

Patients must be offered participation in these molecular correlative studies. With the patient's consent, tissue and blood specimens will be submitted as outlined below. Samples will be de-identified and coded with a new patient ID number to protect patient's identity.

Specimen Collection, Storage, Shipping and Submission Requirements

It is required that paraffin-embedded tissue blocks or slides from time of diagnosis (or subsequent, but prior to therapy) as well as blood specimens, as outlined below, be submitted for expression of relevant molecular targets.

- **Archival tumor specimens:** If available, 1 - 2 paraffin-embedded tissue blocks containing formalin-fixed tumor or needle aspirate slides from time of diagnosis (or subsequent, but prior to therapy) should be submitted for evaluation of expression of PD-L1 and other relevant molecules. Paraffin blocks may be processed according to standard institutional protocols. If blocks are unavailable, 16 unstained slides are acceptable alternatives.
- **Fresh tumor biopsy:** **All specimens must be labeled with protocol number, patient registration number, and date of specimen collection.** Tissue portions will be used for (in order of priority):
 1. Fixed in formalin for the preparation of FFPE blocks
 2. Placed in 1 ml RNA later and snap frozen with liquid nitrogen and stored at -70 to -80°C for future RNA extraction and qPCR and immunochip analysis,
 3. Snap frozen with liquid nitrogen and stored at -70 to -80°C for future DNA extraction
- **Blood specimens:** Blood specimens (3 x 10 ml lavender top EDTA tubes) will be collected from each patient.

Each purple-top (EDTA) tube should be delivered to the lab where it will be inverted several times, and placed on wet ice until centrifugation. The tubes should be centrifuged as soon as possible at approximately 600 x g for 10 minutes. Approximately 1.5 ml of plasma should be removed from each tube and pooled in a fresh, sterile 15 ml conical tube. Centrifuge plasma a second time at 1500-1600 x g for 5 – 10 minutes to pellet and remaining cells. After the second spin, plasma should be removed and placed in 500 ul aliquots in labeled cryotubes. Plasma will be frozen and stored at -70 to -80°C. Plasma samples will be assayed by Luminex to evaluate systemic cytokine levels.

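### The sample totals in Section 8.2 and the power statement in Section 9.6 fit about 46 patients, but the trial is capped at 25; the blood schedule and the mandatory status of samples also need reconciling.

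*Combined protocol and SAP*

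**What the plan says.** **Totals.** Section 8.2 states that "tumor tissue will be obtained pre- and post- treatment" and that "peripheral blood will be obtained pre-treatment and at two time points post-treatment from each patient". From this it concludes that "a total maximum of 92 fresh tumor biopsies and 138 blood samples will be obtained for this study". Section 8.1 confirms two biopsies: "Tumor biopsies will be obtained pre-treatment and during the final intralesional needle placement for IL-2 delivery". Sections 8.1, 8.2.1 and 8.2.2 also describe three blood time points.

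**Enrolment.** Section 2.0 says: "A total maximum of 25 patients will be enrolled". Section 1.0 gives the same maximum. Section 9.1 also gives 25, but counts evaluable patients.

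**Blood schedule.** The study calendar (Section 6.1, footnote k) places research blood at cycles 1 and 2, cycle 2 week 3, cycle 3 and cycle 6, then at every sixth cycle.

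**Power.** Section 9.6 claims at least 80% power for a correlation of 0.4 at a two-sided 0.05 level. It does not state the number of patients behind that claim.

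**Status of samples.** Section 5.2 says that "patients will undergo mandatory treatment lesion biopsies and blood draws pre-treatment and during the needle placement for the final IL-2 treatment", and Section 8.1 refers to "mandatory serial patient blood and tumor samples". Appendix 3 says: "Patients must be offered participation in these molecular correlative studies", with specimens submitted on the patient's consent. Its next paragraph says that archival tissue and blood specimens are required, and does not name fresh biopsies.

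**The concern.** The two totals are presented as the product of patients and samples per patient, yet the number of patients they imply is almost twice the enrolment cap. The same mismatch affects the one quantitative claim made for the translational work, the power in Section 9.6. A reader relying on Sections 8.2 and 9.6 would expect a larger sample base and a more sensitive correlation analysis than 25 patients can give.

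The blood schedule and the status of the samples matter for a related reason. The number of usable pre/post sets depends on which draws are planned and on whether every patient must provide them. Section 8.2 refers to Appendix 3 for sample collection, so the wording there guides what sites do.

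**Working it through.** **Inputs**
- Biopsies per patient: 2 (Sections 8.1 and 8.2; calendar footnote i).
- Blood samples per patient: 3 (Sections 8.1, 8.2, 8.2.1, 8.2.2).
- Enrolment cap: 25 (Sections 1.0, 2.0, 9.1).
- Phase I: up to 18. Phase II: 21 including 3 from phase I (Section 9.1), or 18 additional patients (Section 2.0).
- Power claim: r = 0.4, two-sided 0.05, at least 80% (Section 9.6).

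**Step 1: reproduce the totals.** Samples = patients × samples per patient. Solving for patients gives 92/2 = 46 and 138/3 = 46. At the cap, 25 × 2 = 50 and 25 × 3 = 75. The stated totals are 92/50 = 138/75 = 1.84 times what the cap allows.

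**Step 2: try other patient numbers from the documents.**

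| Patients | Basis | Biopsies (×2) | Bloods (×3) |
|---|---|---|---|
| 21 | phase II total | 42 | 63 |
| 25 | cap | 50 | 75 |
| 36 | 18 + 18 | 72 | 108 |
| 39 | 18 + 21 | 78 | 117 |
| 42 | four dose levels × 6, plus 18 | 84 | 126 |
| 46 | solved from the totals | 92 | 138 |

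Only 46 reproduces the totals, and it reproduces both.

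**Step 3: try other schedules at 25 patients.** Section 4.11 mentions tissue at progression as well. Three biopsies each would give 75, still below 92. For blood on the calendar:
- 4 draws through cycle 3: 25 × 4 = 100.
- 5 draws through cycle 6: 25 × 5 = 125.
- 6 draws through cycle 12: 25 × 6 = 150.

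**Step 4: check the power statement.** By Fisher's z, power ≈ Φ(atanh(r)·√(N − 3) − 1.96), with atanh(0.4) = 0.4236.
- N = 46: 0.4236 × √43 = 2.778; Φ(0.818) = 0.79.
- N = 25: 0.4236 × √22 = 1.987; Φ(0.027) = 0.51.
- N = 21: 0.4236 × √18 = 1.797; Φ(−0.163) = 0.44.
- N for 80%: ((1.960 + 0.842)/0.4236)² + 3 = 46.7, so 47.
- Detectable r at N = 25 with 80% power: tanh(2.802/√22) = tanh(0.597) = 0.535, about 0.54.

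A simulation of 100,000 bivariate normal samples, using the t-test of Pearson's r, gave 0.80 at N = 46, 0.53 at N = 25 and 0.45 at N = 21. The claim therefore sits at the 80% line for 46 patients and is far from it at 25.

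**Step 5: set the wording on status side by side.** Sections 5.2 and 8.1 say mandatory for both tissue and blood. Appendix 3 first describes an offer of participation, then a requirement for archival tissue and blood. For blood it says both things. For fresh biopsies only the offer wording applies.

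**The case against.** The endpoints are described in Section 9.6 as exploratory and hypothesis generating, the totals are maxima, and no analysis uses 92 or 138 as a denominator. That stands, and it limits the weight of the point. It does not rescue the figures: Section 8.2 derives them from its own schedule, and the power claim in Section 9.6 is a separate statement that fails at 25 patients.

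The figure of 50 biopsies is not beyond question either. Section 4.11 mentions tissue at progression, and Section 9.1 caps evaluable patients while Sections 5.4.1.1 and 5.9 provide for replacing patients not evaluable for DLT. Both must be settled first. Neither reading reproduces 92: three biopsies each give 75, and reaching 46 patients would take 21 beyond the cap.

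Four stronger readings are tempting but not supported:
- A reader might infer that 138 blood samples fits no schedule. The calendar is open-ended, and 138 lies between its totals of 125 and 150 for 25 patients. The firm point is only that the three time points in Section 8 differ from the calendar.
- A reader might infer that Appendix 3 makes sampling optional, so that the pairs come from volunteers only. Consent is needed for mandatory research samples too, and the appendix goes on to say that archival tissue and blood are required. Inclusion criteria 12 and 13 (signed consent, ability to comply) partly cover agreement. What patients are told cannot be checked, because consent pages were removed before review.
- A reader might count reduced power for paired pre/post changes as a broken claim. The plan makes no power statement for those tests.
- A reader might take the common fit to about 46 as proof of carry-over from a larger design. That is plausible, but the documents do not say so.

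**Conclusion.** The concern holds in this form. The totals in Section 8.2 require exactly 46 patients against a cap of 25, and overstate the available material by a factor of 1.84 on that section's own schedule. The power statement in Section 9.6 is not met at the cap: about 0.51 (0.53 by simulation) instead of at least 0.80 for r = 0.4, with about 0.54 the detectable correlation. These power figures assume bivariate normal data, Pearson's correlation and one complete value from each of 25 patients; missing samples would lower them.

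The blood schedule differs between Section 8 and the calendar. The status of samples is unclear rather than plainly optional: Sections 5.2 and 8.1 say mandatory, and Appendix 3 is internally mixed. Bias from self-selection would arise only if sampling proves to be voluntary.

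This should be corrected, but it concerns exploratory endpoints. The primary endpoint, the MTD assessment and the phase II decision rule do not depend on it.

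**What to change.** 1. Settle whether tissue at progression (Section 4.11) is planned and whether the cap counts enrolled or evaluable patients (Sections 1.0 and 2.0 against 9.1). With two biopsies and 25 enrolled patients, restate Section 8.2 as at most 50 biopsies.
2. Reconcile the blood time points in Sections 8.1, 8.2, 8.2.1 and 8.2.2 with the calendar in Section 6.1, then recount. Three draws give 75; the calendar gives 100 through cycle 3, 125 through cycle 6 and 150 through cycle 12.
3. In Section 9.6, state the number of patients and give either the power for r = 0.4 at that number or the correlation detectable with 80% power.
4. Make Sections 5.2 and 8.1 and both sentences of Appendix 3 agree on whether fresh biopsies and blood are mandatory. If they are voluntary, add a comparison of baseline features between patients with and without paired samples.

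The cost is wording in these sections, plus one descriptive table if sampling is voluntary. No patients or procedures are added. The stated sample base and power become smaller.
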